After the end of the implementation phase, in-depth interviews with a random sample of stakeholders: 20 patients who initiated PrEP via telemedicine (recruited from our current TelePrEP study and from UMMC associated clinics), 5 PrEP-eligible patients from our study who did not receive PrEP, and 5 providers / staff who are involved in telemedicine for PrEP will occur to yield interview data on acceptability and feasibility of the protocol and the facilitators and barriers to wider implementation of Tele-PrEP-MS. These interviews will focus on similar factors including community context; organizational characteristics, culture and climate; leadership; dynamics of the CBO team; individual characteristics and attitudes; training monitoring and support; protocol fit; and fiscal viability. All interviews will be done by phone at the end of the study period by a trained staff in RI. Interviews will be digitally recorded and kept in a secure location on the Rhode Island Hospital server.

Clinical Trials Registration and Results Dissemination Plan. This study will be registered on ClinicalTrials.gov in accordance with NIH policy. Consent forms will include language informing participants of the project's registration and submission of results to ClinicalTrials.gov. No participant identifying information will be submitted.

Linkages to Subjects and Access to Subject Identities

For each stage of the research study, participant names and contact information will be maintained in a recruitment/enrollment database. Once individuals enroll in the study, names will be linked to a participant ID number in this database, which will be kept in a restricted access folder on a secure server. All name/ID number files will be assigned a code name unrelated to the name of the study. Signed consent to contact forms will also be kept in a locked file cabinet, separate from any other project data. Once data collection is completed, the corresponding recruitment/enrollment database will be deleted as it is unnecessary to maintain the link between participant identity and study data. Destruction of these databases must be witnessed and documented on the Master List Verification of Destruction document, which will be maintained in a regulatory file. Furthermore any information collected as part of this study will be accessible only to research staff that has completed mandatory training in the protection of human subjects.

Potential Risks

The risks for this study for patients are considered minimal. Every effort will be made to ensure that study participants are protected from risks. The risks are as follows: 1) potential coercion; 2) loss of confidentiality; 3) emotional discomfort during the assessments; and 4) risk associated with learning they have HIV, if that is diagnosed during the course of the study. The protection against each risk is described in detail below under Adequacy of Protection Against Risk.

The risks for this study for other stakeholders such as CBO staff and PrEP clinicians are also considered minimal. Every effort will be made to ensure that study participants are protected from risks. The risks are as follows: 1) potential coercion; 2) loss of confidentiality; and 3) emotional discomfort during the interview. The protection against each risk is described in detail below under Adequacy of Protection Against Risk.

Adequacy of Protection Against Risk

Recruitment and Enrollment. The risk of possible coercion will be minimized by following standard procedures for recruiting and enrolling participants. All PrEP-eligible adults over the age of 18 presenting for HIV testing at the CBO sites during the trial will be approached for recruitment and given a Consent to Contact form for the online surveys. The Consent to Contact form will include: name, email address, and phone number. Consent to contact forms will be securely faxed to University of Mississippi Medical Center (UMMC) staff, who will follow up with interested parties by phone or email. Similar procedures are already being used by CBOs to send forms containing PHI to the Jackson UMMC site. Those who wish to participate will receive a

DocuSign consent form via email from the UMMC RA, which will outline study aims and procedures, and language regarding the risks/benefits of participating in a research study. It will also state that by electronically signing, they are allowing UMMC study staff to view their medical records relevant to PrEP and to contact them after the last survey for participation in a phone interview. Participants can decline the phone interview but still participate in the surveys. This online survey data will be de-identified and kept on a password protected participant log on a secure drive. Participants will be given ample time to consider risks of participation and have the option of talking to research staff by phone to discuss any questions. Participants will also be reminded that study participation is voluntary and that refusing to participate or withdrawing from the study at any time will not result in any negative consequences.

Recruitment of stakeholders (i.e. staff members at community based organizations and PrEP specialists) in the formative phase or post-implementation phases of the study will involve being contacted by investigators to participate in interviews. Stakeholders will be reminded that they are not obligated to participate in this project by virtue of their employment and they are free to withdraw at any time without jeopardy to their position.

Protections Against Risk

Breach of Confidentiality. Potential risk will be minimized by strictly adhering to the guidelines for research outlined by the site IRB, state laws, the Federal Health Insurance Portability and Accountability Act of 1996 and its regulations ("HIPAA"), and the DHHS Federal Policy for the Protection of Human Subjects (45 CFR Part 46 Subpart D). This will include identifying participant research data by numeric ID only and maintaining any records containing potentially-identifying information separate from any research data. All research data (written records and audiotapes of program sessions) will be kept in a locked file and electronic data will be password-protected. All of these study-related materials will only be accessible to research staff. No names, only identification codes, will be used in presenting data in lectures, seminars, and papers. Information will be released only with written consent of the participant.

Participant confidentiality will be breached only to protect the safety and welfare of research participants and only in accordance with state and federal law. If abuse is reported, a report will immediately be filed with the appropriate state department or agency. See "Emotional Distress" below for more details on the available clinical services.

Questionnaire data collection for the implementation phase will include a baseline assessment (completed upon enrollment) and assessments at 3- and 6- months post-enrollment. Participants will receive the three assessments, as online REDCap surveys, via email. **No PHI will be collected in these assessments.**

REDCap online survey software will be utilized for the collection of data from participants, from which data are easily extracted for entry to statistical programs (e.g., SPSS). **The research team will develop documentation for each survey measure, including appropriate branch and skip logic, as well as a codebook with documentation for each variable.** Staff will program surveys using the REDCap survey platform. **Basic survey content will be programmed first and then survey flow and logic will be programmed after content has been reviewed and edited.** Survey-based reporting mechanisms will be programmed, including automated invitation and reminder emails for participants as well as triggered emails to staff for the purposes of monitoring and reporting. Usability testing by trained staff will be conducted and will include checks for basic grammar, spelling, sequence, and comprehension. Further advanced testing will be conducted in order to test the survey's logic and flow; this advanced testing phase will include the generation of test data to ensure all branch and skip logic works as planned within the variable codebook. Throughout the course of the project, regular data downloads will be conducted to check the quality and accuracy of the data, to ensure no data are missing, and to regularly report on the sample characteristics. **REDCap meets or exceeds all HIPAA and HITECH requirements for security and privacy.** Following data transfer, syntax will be developed to arrange the data for quantitative analysis. Directories describing data files, variable label codebooks, and data routines will be

developed during the year-2 trial. Following that, data will be extracted and archived on a monthly basis. Routines for assessing data integrity will be developed, with procedures established for accepting, correcting, or rejecting data. All data will reside on servers behind firewalls (with access restricted to study personnel) and on computers with hospital security enabled. All servers are routinely backed daily (to off-site locations), and the project will create its own weekly backups on secure external drives kept both on and off site. Any transfer of data among the study sites will be done using secure methods (e.g., secure FTP).

All study personnel names on this application have completed training and received certification in Human Subjects Research Protection (CITI Program) and HIPAA regulations. They will continue to renew this training in compliance with hospital policies.

For the formative interviews in PY01 and the post-implementation interviews in PY3, participants will be asked to provide informed written consent to audiotaping at the time of study entry. To assure confidentiality and protection of the participants, interviews will be digitally recorded and kept in a secure location on the Rhode Island Hospital server. Only research staff will have access to the audio files for review of the interviews.

Emotional Distress. We will minimize distress by presenting questions in a supportive manner, assuring participants that they may refuse to answer any questions that make them uncomfortable, and may terminate participation in the study at any time. All participants may receive medical or mental health treatment at any time during the study. Clinical need will determine whether it is appropriate for the participant to stop continuation in the study. If stakeholders experience distress or concerns, they will be able contact one of the PIs to discuss any concerns for themselves for their role in the project. They will be able to discontinue participation in the project at any time if desired.

All patient participants will be HIV negative as tested by the CBO and we anticipate that very few participants will later test positive for HIV; however, those who test positive may feel extreme distress when learning of their diagnosis. For those who test positive to HIV, they will be counseled by clinic staff in private by in accordance with CDC's HIV testing and counseling guidelines. The diagnosis and counseling provided will involve first reviewing the type of test that was administered, giving them their test results, explain the meaning of the test result, ask if they have any questions, comments or concerns, talk about resources, discuss the participant's feelings and assess their readiness to leave the location, secure additional support and resources for the youth if necessary, and provide them with additional information if necessary. All participants will be linked to the University of Mississippi Medical Center HIV clinic to ensure they get confirmatory testing and that they are enrolled in HIV treatment services. If an appointment in the HIV clinic is not immediately available, then clinic staff will maintain contact with the subject until they have been evaluated by the HIV clinic. The result will be reported to the Department of Health as per state regulations. [name] and staff are expert HIV medical care providers and are experienced in assisting those newly diagnosed with HIV.

If a participant reports feeling distressed, or has any acute concerns, as a result of their involvement in any phase of the research project (i.e. enrolling, baseline assessment, interview session, Tele-PrEP-MS session, follow-up), clinical resources will be offered. If a participant contacts study staff because of distress or concern due to participation in the study or directed activities that occur away from the clinical space, he will be assessed first over the phone, and then, if needed, as described below.

During any phase of the study, if research staff determines that a participant is an acute medical or psychiatric risk, [name] or a licensed designee will meet with them individually for further assessment. Acute risks would include severe medical illness, or the development of any other severe psychiatric symptoms or disclosure of sexual or physical abuse. Any participant who exhibits acute risks will be evaluated immediately by emergency room clinical staff or if less acute, by an independent clinician that day. Less severe medical needs or distress can be managed by staff or [name] over the phone or with an individual interview. [name] and/or staff will meet with participants and/or families to review concerns and to make referrals for continuing care as needed. Of note, members of the proposed research team have substantial prior clinical (medical and psychiatric) and

research experience in care of PrEP-eligible and HIV-infected individuals as evidenced through their biographical sketches.

Potential Benefits of the Proposed Research to the Subjects and Others

Importance of Knowledge to be Gained. All phases of the proposed study will provide important information for the development of Tele-PrEP-MS protocols for PrEP-eligible individuals in underserved areas. We hope that our study will be successful in overcoming barriers of access to PrEP services in these areas and think that the clear examination of these questions outweighs the previously mentioned risks. Given the significant risk of HIV infection in the Southern United States and the lack of easily accessible PrEP services in Mississippi, the knowledge to be gained from this research is significant. The risks to participants are reasonable in relation to the importance of the knowledge to be gained.

Reimbursement for Time and Effort. Participants (10-20 HIV testing clients) will be reimbursed with a \$40 gift card for focus group participation. Stakeholders (4 CBO HIV testing staff, 4 CBO administrators, 3 PrEP specialists) will be reimbursed with a \$40 gift card for focus group participation. Participants in the Tele-PrEP-MS Trial (240 HIV testing clients) will be reimbursed with a \$25 electronic gift card for the baseline assessment, and \$30 electronic gift cards for both the 3-month and 6-month follow-up assessments. In Year 3, stakeholders (25 patients, 5 CBO HIV testing staff/, CBO administrators/ UMMC PrEP specialists) will be reimbursed with a \$40 electronic gift card, for their time and effort..

DEPARTMENT OF HEALTH AND HUMAN SERVICES (DHHS) “REQUIRED EDUCATION IN THE PROTECTION OF HUMAN RESEARCH PARTICIPANTS”

Since October 1, 2001, Lifespan, which is the nonprofit health care system of which Rhode Island Hospital is a part, has required that researchers and IRB members read Protecting Study Volunteers in Research (Dunn & Chadwick) and complete the related exam. This process has served as initial certification between 10/2001 and 5/2005. In June 2005, the Office of Research Administration contracted with CITI, a Collaborative Institutional (modular) Training Initiative program, for our Human Subjects protection and HIPAA training for all research personnel. Currently this program offers our researchers a basic human subject's protection course as well as a refresher course, which is required every three years. Documentation of successful completion is automatically generated and is printed directly by the researcher. For further information regarding Lifespan's Human Subject's Protection course go to: <http://www.lifespan.org/research/IRB/MandatoryEdguidance.asp>. Additional and continuing education opportunities for clinical researchers include the Office of Research Administration newsletter that is circulated to > 900 recipients every 6 weeks. Relevant information concerning research review is available on the ORA web page at www2.lifespan.org/research/. In addition to standard institutional research information, the web page contains links to other sites such as CenterWatch, NIH, PRIM&R/ARENA. Investigators and staff at all sites receive similar training and certification.

Resource and Data Sharing Plan.

Sharing of data generated by this project is an essential part of our proposed activities and will be carried out in several different ways. We will make our research available to the community of researchers interested in this topic to avoid unintentional duplication of research. After the results are analyzed, the information and results will be made available through presentations at national scientific meetings. We will distribute the results through the Center for AIDS Research Social and Behavioral Sciences Research Network for investigators who are interested in this topic. The results will also be made available through publications in scientific journals appropriate to the project's subject area. If the results appear promising, we will share the protocol and training manual with other relevant and interested clinics and community based organizations and it can be distributed through the Centers for AIDS Research and AIDS Trials Networks. We will also distribute the manual and procedures to other relevant community based organizations with the assistance of My Brother's Keeper (MBK), the organization working with us on this project. MBK has connections and affiliations with similar community organizations throughout this South and will facilitate dissemination of the findings.

Clinical Trials Registration and Results Dissemination Plan

Investigators at Rhode Island Hospital (RIH) will be responsible for the registration and submission of results for this project on ClinicalTrials.gov as outlined in the NIH policy (NOT-OD-16-149). The senior research assistant will work with the department research administrator and the P.I. to ensure that this project is registered within 21 calendar days of enrollment of the first participant. Results will be submitted to ClinicalTrials.gov within one year of the trials' primary completion date. Additionally, all consent forms, will include standard language related to posting of project results on ClinicalTrials.gov. Consent forms, containing the language below, will be submitted and IRB-approved prior to participant enrollment.

"Additionally, a description of this clinical trial will be available on <http://www.ClinicalTrials.gov>, as required by U.S. law. This Web site will not include information that can identify you. At most, the Web site will include a summary of the results. You can search this Web site at any time."

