Tele-PrEP-MS Trial (Aim 2 - Year 2): Implement Tele-PrEP-MS in MS CBOs.

Recruitment and enrollment (see Human Subjects): All PrEP-eligible adult clients who present for HIV testing in the participating CBOs (not near UMMC) during the months of Aim 2 will be eligible to be enrolled in the online feasibility, acceptability and implementation survey. As noted in Aim 1, CBO staff will be trained in procedures to assist clients in obtaining necessary financial, transportation, and logistic resources for PrEP. They will collaborate with UMMC staff to resolve these issues for participants as they did in our recent Tele-PrEP-MS experience at a CBO.

PrEP Care Cascade estimates: Based on data from the CBO testing sites, UMMC HIV screening clinics, and our recent Tele-PrEP-MS experience in a CBO (see Preliminary Studies), it is estimated that a total of 600 adults (both sites combined, 25 per month at each month for 12 months) will present for HIV testing during Year 2. It is estimated that 300 (50%, which is less than the UMMC rate) will be PrEP-eligible (not HIV infected and with elevated risk scores). Because of COVID, the CBOs have discontinued the in-person events that led to most of their HIV testing. With permission of our NIMH program officer, [name], our survey recruitment goal was reduced from 240 PrEP-eligible to 25-50 and Aim 3 (qualitative assessment) was enhanced. We will enroll 25-50 (80%) of the PrEP-eligible in the assessments ⁽⁸⁴⁾. The sample will be 75% male (mainly MSM), 85% will be nonwhite, with mean age of 26 years. Of the 25-50 enrolled participants, 75%, which is less than our recent experience, will attend Tele-PrEP-MS with UMMC specialist, and 66.6%, which is less than our recent experience and more than the UMMC rate, will return within three months and will be taking PrEP. Adherence at 6 months will also be assessed.

Determinations of Tele-PrEP-MS acceptability and its associated factors (Aims 2 & 3, Year 3):

Aim 3: Determine the acceptability and feasibility of Tele-PrEP-MS and to examine the individual, organizational and structural factors associated with its acceptability and feasibility.

Analyses will occur with a mixed methods approach that includes interviews of stakeholders (clients, staff, and administrators), an online survey of clients obtained during the implementation phase in Aim 2, and aggregate clinic records.

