Aim 2: Determine the acceptability of Tele-PrEP-MS and to examine the factors associated with its acceptability. The Client Satisfaction Questionnaire (CSQ), the Session Evaluation Form (SEF) and the Working Alliance Inventory (WAI) will quantitatively assess acceptability according to patients attending Tele-PrEP-MS. In addition to scale scores, individual item mean scores and standard deviations will be reviewed to determine if there are specific elements of the protocol that are lacking in feasibility, appeal, relevance, or utility. Other scale scores (e.g. Motivation for PrEP) will be computed and non-scale items topically grouped (e.g. health literacy, housing).

Aim 3a: Examine PrEP-related outcomes over six months (proportions screened for PrEP eligibility; attending a PrEP medical evaluation; taking PrEP at 3 and 6 months) **to compare the academic medical center and the CBOs** (Exploratory). The UMMC HIV/STI screening clinics test 9,000 patients each year and approximately 65% are at high-risk for HIV (according to on-going analyses of the Risk Stratification data). Only one third return to initiate PrEP because wait times and distance are often barriers. These rates will be updated at UMMC for the trial year of this study and will be used to gauge the efficiency PrEP outcomes observed in Tele-PrEP-MS at the CBOs. As this is an exploratory aim, direction of effects is not predicted and the comparison is largely descriptive and to provide context for the results. Comparisons of proportions will be made using Chi Square analyses.

Aim 3b: Examine any factors related to these outcomes (Exploratory aim). Only the CBOs will have patient-level data to examine factors related to patients' PrEP outcomes. Relevant scale scores (e.g. Motivation for PrEP) will be computed and non-scale items topically grouped (e.g. health literacy, housing). Outcomes include Tele-PrEP-MS visit attendance (yes/no; clinic and self-report data), PrEP prescription accepted (yes/no; clinic and self-report), and adherence to PrEP (yes/no; clinic and self-report). For the enrolled PrEP-eligible group multiple logistic regression will be used to examine the predictive association of demographics (e.g. race, sexual orientation), baseline scales (e.g. motivation, skills), scale change scores (e.g. PrEP knowledge), and screening visit acceptability (CSQ, SEF, WAI scores) on each outcome.

Inclusion of Women, Minorities, and Children

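### Does Aim 3a need a rewritten analysis because it does not say whether the CBO proportions set against UMMC come from consented enrollees or from all clients?

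*Combined protocol and SAP*

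**What the plan says.** In the Quantitative Data Analytic Plan, Aim 3a sets out three kinds of proportion to compare between UMMC and the CBOs: screened for eligibility, attending a PrEP evaluation, and on PrEP at 3 and 6 months. On the UMMC side, "These rates will be updated at UMMC for the trial year of this study and will be used to gauge the efficiency PrEP outcomes". The method is one sentence: "Comparisons of proportions will be made using Chi Square analyses". The status of the comparison is also stated: "As this is an exploratory aim, direction of effects is not predicted and the comparison is largely descriptive". No CBO denominator or data source is given.

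The next paragraph, Aim 3b, does name its analysis set: "For the enrolled PrEP-eligible group multiple logistic regression will be used".

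The Aim 3 introduction, just after the PrEP Care Cascade estimates, lists three sources: stakeholder interviews, the client survey and aggregate clinic records. It does not assign them to sub-aims.

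The cascade estimates use both bases. Eligibility is projected among everyone tested: "300 (50%, which is less than the UMMC rate) will be PrEP-eligible". PrEP use is projected among enrollees: "66.6%, which is less than our recent experience and more than the UMMC rate, will return within three months and will be taking PrEP". The enrolment target reads "We will enroll 25-50 (80%) of the PrEP-eligible in the assessments".

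**The concern.** Two analysts following Aim 3a could put different CBO groups into the same chi-square.

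- **Service counts.** One analyst would take all tested or all eligible clients from clinic records. Consent then plays no part.
- **Enrollees.** The other would take the 25 to 50 people who signed consent. Several sections point this way for the later steps. The Subjects paragraph under Quantitative assessments, the Primary outcomes, the Sources of Material section and the Recruitment and Enrollment section all describe attendance, PrEP receipt or record access for people who have signed.

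UMMC's figures are clinic-wide rates with no consent step described. People who agree to three surveys about PrEP may be more inclined, or less, to take it. Under the second reading, a gap between the CBOs and UMMC could partly reflect who agreed to be surveyed, and a true gap could be hidden in the same way. At stake is how the CBO cascade is read beside UMMC's when wider use of the programme is considered.

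**Working it through.** **1. The plan's own cascade.** From the PrEP Care Cascade estimates: 25 per month × 2 sites × 12 months = 600 tested; 600 × 0.50 = 300 eligible; 300 × 0.80 = 240, the original goal. All three reproduce. The current goal of 25 to 50, read with the retained 80%, implies 25/0.80 = 31 to 50/0.80 = 63 eligible clients. If the attendance and PrEP-use rates are sequential, projected uptake is 0.75 × 0.666 = 50% of enrollees.

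**2. Which reading the text supports.** Enrollees are all PrEP-eligible already, so the proportion screened cannot be computed from them and needs clinic-level counts. Aggregate records are a listed Aim 3 source, and the restriction to enrollees is written for Aim 3b only. The sections on consented participants describe data collection that Aim 3b needs in any case. The 66.6% figure is a planning projection, not a definition of an analysis set. For attendance and PrEP use, however, the source stays open.

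**3. Size of the selection effect if enrollees are used.** Inputs:

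- UMMC, from Aim 3a: 9,000 × 0.65 = 5,850 high-risk, of whom one third is 1,950.
- Assumed, because the documents give no figure: no true difference (P = 1/3 among all eligible CBO clients), a two-sided 0.05 threshold, and an odds ratio (OR) of uptake in consenters against non-consenters.

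With f the enrolled share, solve f·p1 + (1 − f)·p0 = P, where p1/(1 − p1) = OR × p0/(1 − p0). At f = 0.8 and OR = 2, p1 = 0.362 and p0 = 0.221 (check: 0.8 × 0.362 + 0.2 × 0.221 = 0.333). The enrollee rate is 2.8 points too high.

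The rejection probability is the exact binomial(n, p1) probability that the chi-square against 1,950/5,850 gives p < 0.05:

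| f | OR | p1 | n = 25, plain / corrected | n = 50, plain / corrected |
|---|---|---|---|---|
| any | 1 | 0.333 | 5.6% / 3.1% | 5.1% / 3.5% |
| 0.8 | 1.5 | 0.351 | 7.1% / 3.5% | 5.6% / 4.7% |
| 0.8 | 2 | 0.362 | 8.4% / 4.1% | 6.7% / 6.1% |
| 0.8 | 3 | 0.375 | 10.5% / 5.1% | 9.0% / 8.6% |
| 0.8 | 0.5 | 0.301 | 5.1% / 3.9% | 8.3% / 4.5% |
| 0.5 (assumed) | 2 | 0.409 | 18.0% / 9.5% | 19.2% / 19.2% |

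"Corrected" means with continuity correction.

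**4. Against sampling error.** The 95% half-width around one third is 1.96 × √(0.333 × 0.667/n): 18 points at n = 25 and 13 points at n = 50. At the plan's share and OR = 2, the 3-point shift is a fifth to a sixth of that.

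**5. Bounds with no odds ratio assumed.** For an enrollee rate r, the all-eligible rate lies between f·r and f·r + 1 − f. With r = 0.50 and f = 0.8 this is 40% to 60%, so the lower end stays above one third. Selection alone could explain the whole expected gap only if f fell to 0.333/0.50 = 0.67 or below. If 66.6% applies to all enrollees, the limit is 0.333/0.666 = 0.50.

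**The case for a change.** The strongest case for a change is that exploratory status does not supply a denominator. A test is planned, the sections on data collection lean toward enrollees for attendance and PrEP use, and the 80% share cannot be relied on. It was kept when the goal fell from 240 to 25–50, and the reduced testing volume is not stated. At an assumed 50% share, rejection under no true difference reaches 18% to 19% without correction. UMMC's one third also has no explicit denominator. The remedy looks cheap: define each step and use clinic counts.

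Much of this stands. The source for the later steps is unstated and the true share is uncertain. Three things limit its weight.

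- The larger figures need a share or an odds ratio that no document supports. Dividing 25 to 50 by 300 would give 8% to 17%, but that sets the reduced goal against a count projected before COVID; the plan says "the CBOs have discontinued the in-person events that led to most of their HIV testing".
- UMMC's one third directly follows the high-risk percentage in Aim 3a and the PrEP-eligible percentage in Clinical Settings, so the natural denominator is at-risk patients. The rate is to be updated for the trial year in any case.
- The remedy beyond wording is not clearly cheap. Individual record access is tied to signed authorisation, so counts for non-consenters may need further approval. The plan does not describe whether the three added recruitment organisations can supply them. Barring a test of 3- and 6-month PrEP use where such counts are missing is a debatable choice for a comparison already labelled descriptive.

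**Conclusion.** The omission is genuine but is missing detail, not a wrong rule. Aim 3a carries no alpha, power or decision rule, and the plan says the comparison is there to give context. An analyst would sensibly take the screened proportion from clinic counts, use the aggregate records for later steps where they hold them, and label any enrollee-based rate as such, with the enrolled share beside it.

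If enrollees are used, the shift is about 3 points in either direction at the plan's 80% share (odds ratio 2 or 0.5). For odds ratio 2, rejection is 6.7% to 8.4%, or 4.1% to 6.1% with continuity correction. This rests on an assumed odds ratio, an assumed two-sided 0.05 threshold and the stated 80%; a lower true share would enlarge it. Differences between the CBOs and UMMC in location, access and case mix would remain under either reading, so a tighter definition would still not turn the comparison into an estimate of programme effect. No change to the plan is needed.
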